11.1.2 Imputation of missing/partially missing dates

Missing data will not be imputed unless otherwise specified.

Age: The day is not recorded in the eCRF and will be defaulted to the 1st day of the month specified in the eCRF. If the month field is missing, impute missing day and month as July 1st. If the year field is missing, age will be set as missing.

For safety analyses, incomplete date of last dose of study drug and incomplete start date of a new antitumor treatment for urothelial carcinoma that are missing the day of the month, the 15th of the month will be used to impute the missing data. When imputing partial last dose dates, the last assessment date and death date will be taken into consideration. This imputation rule will be used to determine the treatment-emergent period.

Adverse Events and Concomitant Medications:

The imputation rule for the safety analyses will be used to address the issues with partial dates. The imputed dates will be used to determine the treatment-emergent period. For adverse events with a partial date, available date parts (year, month, and day) of the partial date will be compared with the corresponding date components of the start date and end date of the treatment-emergent period to determine if the event is treatment emergent. When in doubt, the adverse event will be considered treatment emergent by default. The following rules will be applied to impute partial dates for adverse events:

If start date of an adverse event is partially missing, impute as follows:

- If both month and day are missing and year = year of treatment start date, then set to treatment start date
- If both month and day are missing and year \neq year of treatment start date, then set to January 01
- If day is missing and month and year = month and year of treatment start date, then set to treatment start date
- If day is missing and month and year \neq month and year of treatment start date, then set to first of the month
- If start date is completely missing, set to treatment start date as long as adverse event end date is not before treatment start date

If end date of an adverse event is partially missing, impute as follows:

- If both month and day are missing, then set to December 31
- If only day is missing, then set to last day of the month

PFIZER CONFIDENTIAL

CT24-WI-GL03-RF02 2.0 *Non-Interventional Statistical Analysis Plan For Primary Data Collection Study*

01-Jun-2020

Page 27 of 28

- If end date is completely missing, do not impute

When the start date or end date of a medication is partially missing, the date will be imputed to determine whether the medication is prior or concomitant (or both). The following rules will be applied to impute partial dates for medications:

If start date of a medication is partially missing, impute as follows:

- If both month and day are missing, then set to January 01
- If only day is missing, then set to the first of the month

If end date of a medication is partially missing, impute as follows:

- If both month and day are missing, then set to December 31
- If only day is missing, then set to last day of the month

If start date or end date of a medication is completely missing, do not impute.

Diagnosis of urothelial carcinoma

If the diagnosis date of urothelial carcinoma is partially missing, the following rules will be applied to impute partial dates:

- If both month and day are missing and year = year of treatment start date, then set to treatment start date.
- If both month and day are missing and year \neq year of treatment start date, then set to December 31.
- If day is missing and month and year = month and year of treatment start date, then set to treatment start date.
- If day is missing and month and year \neq month and year of treatment start date, then set to the last day of the month.

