### 9.3. Variables

Table 2 shows the information which will be collected in the study.

090177e1a41aac13\Final\Final On: 28-Jul-2025 13:50 (GMT)

Table 2. Information collected in the study and timing of data collection

Data elements	Variables	Timing of data collection		
		Inclusion	6 weeks	3 months, then every three months until end of follow-up
Inclusion	
 
Type of center
 
Eligibility criteria (inclusion/exclusion)
 
Date of provision of information letter
 
	X		X
Characteristics of patients and their cancer before avelumab initiation	
 
Demographics : month and year of birth, sex
 
Patient and Cancer characteristics: 
 
Localisation: upper/lower (bladder, urethra) urinary tract
 
Cancer characteristics: histological subtype including type of variant*, PD-L1 status and FGFR alteration with type of test and CPS score.
 
 
 
Localized cancer: date of diagnosis, type of treatment (adjuvant/neoadjuvant), regimen, dates of start and end, number of ChT cycles, complete response if neoadjuvant.
 
Adv/mUC: date of diagnosis, stage at ChT initiation, metastatic sites at ChT initiation, Karnowski index and ECOG at ChT initiation, type of ChT regimen, dates of start and end, number of ChT
 
	X		X

090177e1a41aac13\Final\Final On: 28-Jul-2025 13:50 (GMT)

	cycles, response at the end of ChT, date of start of partial or complete response if so.			
Initiation of avelumab	
 
• Patients characteristics : ECOG at initiation
 
• Biological exam: neutrophil, lymphocyte, haemoglobin, creatinine clearance
 
• Metastatic sites
 
• Date of first administration, dose
 
• Use of premedication (acetaminophen and antihistamine)
 
	X		X

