1. Patient ≥ 18 years of age
2. Patient with locally advanced or metastatic urothelial carcinoma (irrespective of tumor histology) whose disease has not progressed (ongoing stable disease, partial response, or complete response) following completion of first-line platinum-based chemotherapy and who has been (retrospective), is (retrospective and prospective), will be (prospective) treated with avelumab.
3. For a patient alive at the moment of the inclusion in the study: the patient must be informed of the study, he/she must be given an information letter signed by the investigator and must not be opposed to the collection of his/her data
For a patient who died before the inclusion in the study: the person of trust of the patient must be informed and the patient (during his lifetime) must not be opposed to the collection of his data.
4. Patient benefiting from a social security scheme according to local regulations

Exclusion criteria

5. For a patient alive at the moment of the inclusion in the study: patient without liberty, under tutelage, or unable to give oral consent.
6. Patient enrolled in a prospective interventional clinical trial assessing an investigational product.

Data source:

The data of interest will be reported in an electronic case report forms (eCRF) by the investigator for each included patient, at inclusion and regularly during follow-up, on the basis of the data available in the patients' medical records.

In addition, two questionnaires (ePRO or paper) will be completed by participants who initiated avelumab after the beginning of the study:

PFIZER CONFIDENTIAL

CT24-WI-GL03-RF02 2.0 Non-Interventional Statistical Analysis Plan For Primary Data Collection Study

01-Jun-2020

Page 8 of 28

- *NCCN/FACT FBLSI-18 (Functional Assessment of Cancer Therapy – Bladder Cancer Symptom Inventory) : The FBLSI-18 is a self-administered questionnaire to assess patient bladder cancer-specific symptoms using a ‘core’ set of questions a cancer site-specific bladder subscale. Higher scores indicate a higher degree of bladder symptoms.*
- *EQ-5D-5L (EuroQoL – 5 dimensions 5 level) : The EuroQol EQ-5D-5L is patient-completed generic questionnaire consisting of 2 pages: the EQ-5D descriptive system and the EQ visual analogue scale (EQ VAS) :*

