8.1.3 Analysis of time-to-event data

Kaplan-Meier estimates (product-limit estimates) will be presented together with a summary of associated statistics including the median survival time with 2-sided 95% CIs. In particular, the survival rate at 3, 6, 9, 12, 15, 18 and 24 months will be estimated with corresponding 2-sided 95% CIs. The CIs for the median will be calculated according

PFIZER CONFIDENTIAL

CT24-WI-GL03-RF02 2.0 *Non-Interventional Statistical Analysis Plan For Primary Data Collection Study*

01-Jun-2020

Page 15 of 28

to Brookmeyer and Crowley (Brookmeyer R, 1982) and the CIs for the survival function estimates at the time points defined above will be derived using the log-log transformation according to Kalbfleisch and Prentice (Kalbfleisch JD, 2002) (conftype=loglog default option in SAS Proc LIFETEST) with back transformation to a CI on the untransformed scale. The estimate of the standard error will be computed using Greenwood's formula.

Frequency (number and percentage) of participants with each event type and censoring reasons will be presented.

For each subgroup analysis, comparison of the different modalities to a reference level will be performed using univariate Cox proportional hazard models. Ties will be handled using the Exact option in SAS (Ties=Exact option in SAS PROC PHREG). Results will be expressed in terms of hazard ratios (HR) and a 2-sided 95% CI will be associated to each HR. A HR of 1 equals a lack of association, a HR greater than 1 suggests an increased risk compared to the reference level, and a HR below 1 suggests a decreased risk.

Time of follow-up for each event (OS and PFS)

A Kaplan-Meier estimation for follow-up duration will also be generated to assess the follow-up time reversing the censoring and event indicators.

Handling of left truncation and right censoring:

The overall survival from the first injection of the chemotherapy used in 1st line will cover

a retrospective and/or prospective data collection period. The time to event of interest ("survival" time) or censoring if no event occurs (right censoring) will be based on the 1st line of chemotherapy start date at a time-point preceding the study entry (avelumab start date). As a result, only participants who are still alive are included in the study.

Therefore, the time from 1st line of chemotherapy start date to avelumab start date is called immortal time and corresponds to a left truncation in survival analyses.

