8.2.2 Secondary criteria analyses

8.2.2.1 Overall survival 2

For OS since chemotherapy initiation, endpoint will be analyzed using survival analysis method, using the same censorship as for primary criterion (Table 1), in the FAS. The starting date to be used is the date of first intake of chemotherapy as reported in the medical history. To avoid any immortal time bias between first intake of chemotherapy and the start of study treatment (avelumab), a modified Kaplan-Meier estimator will be provided using right censoring and left truncation, stabilising the estimates when small samples ($n < 5$) are present (Lai and Ying method – See section 8.1.3).

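### SAP 11.1.2 can impute a partial diagnosis date to a day after the first-line chemotherapy that must precede avelumab; the effect is confined to descriptive use of that date

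*SAP*

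**What the plan says.** The last block of SAP 11.1.2 gives four rules for a partly missing date of urothelial carcinoma diagnosis.

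- Year known and equal to the year of treatment start: "If both month and day are missing and year = year of treatment start date, then set to treatment start date".
- Year known but different: the rule ends "year of treatment start date, then set to December 31".
- Month and year known and equal to those of treatment start: "If day is missing and month and year = month and year of treatment start date, then set to treatment start date".
- Month and year known but different: the rule ends "month and year of treatment start date, then set to the last day of the month".

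Section 11.1.2 does not define treatment start. Elsewhere the SAP means avelumab: section 8.2.2.1 writes "the start of study treatment (avelumab", with the bracket closing there, and section 8.2.1 counts OS from first intake of study treatment.

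On the order of events, inclusion criterion 2 (SAP 2.1) admits patients without progression "following completion of first-line platinum-based chemotherapy". SAP 8.1.3 describes the "1st line of chemotherapy start date at a time-point preceding the study entry (avelumab start date" in the same bracketed way.

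Protocol 9.3, Table 2, collects "Adv/mUC: date of diagnosis, stage at ChT initiation" and, further along the same entry, the start and end dates of first-line chemotherapy. A separate diagnosis date, with treatment dates, is collected for localized cancer. The SAP does not say which of the two diagnosis dates its rules cover.

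**The concern.** Anchoring a missing diagnosis date on treatment start is natural when study treatment is the first therapy after diagnosis. Avelumab here is maintenance. Diagnosis comes first, then a course of platinum chemotherapy, then avelumab. None of the four rules looks at the chemotherapy dates; the only upper limit they respect is avelumab start. They can therefore return a sequence that the eligibility criteria exclude.

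Each rule also picks the latest date compatible with the known date parts and avelumab start. The errors share one sign and do not average out. Any reported time since diagnosis would be too short, and any diagnosis-to-chemotherapy interval could come out negative.

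**Working it through.** The plan states no figure to reproduce. The check applies the four rules to dated sequences.

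**By logic alone**

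- *Same-year rule.* Imputed diagnosis = avelumab start. Chemotherapy ended before that day, so the imputed diagnosis always follows chemotherapy. No assumption is needed beyond eligibility.
- *31 December rule.* If chemotherapy started in the diagnosis year, 31 December falls after its start (level with it if it began that day). It falls after its end only if chemotherapy also finished that year. If diagnosis was in a year before chemotherapy, the order is preserved, though the interval is shortened.
- *Month-end rule.* It can fall after chemotherapy start when diagnosis and first dose share a calendar month. It does not realistically reach the end of a course.
- *Same-month rule.* It needs diagnosis, a whole chemotherapy course and avelumab start in one calendar month. It should almost never apply, and a match would point to a recording error.

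**Worked sequences** (illustrative dates)

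| True diagnosis | Chemotherapy | Avelumab | Missing | Imputed | Days late | Diagnosis to chemotherapy, true → imputed |
|---|---|---|---|---|---|---|
| 15 Jan 2021 | 10 Feb–26 May 2021 | 28 Jun 2021 | month, day | 28 Jun 2021 | 164 | 26 → 26 − 164 = −138 |
| 10 May 2021 | 7 Jun–11 Oct 2021 | 3 Jan 2022 | month, day | 31 Dec 2021 | 235 | 28 → 28 − 235 = −207 |
| 20 Nov 2020 | 10 Dec 2020–25 Mar 2021 | 25 Apr 2021 | month, day | 31 Dec 2020 | 41 | 20 → 20 − 41 = −21 |
| 10 May 2021 | 20 May–23 Sep 2021 | 25 Oct 2021 | day | 31 May 2021 | 21 | 10 → 10 − 21 = −11 |

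In the first row, time since diagnosis at avelumab start becomes 0 instead of 164 days.

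**How often, for an advanced-disease diagnosis**

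The documents give no lags or cycle lengths, so these are assumptions:

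- L, diagnosis to first dose: 14, 28 or 56 days.
- C, first to last dose: cycle length × (cycles − 1), with 21- or 28-day cycles and 4 or 6 of them. This runs from 21 × 3 = 63 to 28 × 5 = 140 days.
- G, last dose to avelumab: 21, 49 or 84 days, one value in each delay category of SAP 5.3.
- Avelumab starts on each of the 365 days of one year.

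Month and day missing:

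- Imputed after chemotherapy start: 1 − (L + 1)/365. This gives 1 − 15/365 = 96%, 1 − 29/365 = 92% and 1 − 57/365 = 84%.
- Imputed after chemotherapy end: 1 − (L + C + 1)/365. The extremes are 1 − 78/365 = 79% and 1 − 197/365 = 46%.
- Imputed exactly at avelumab start: 1 − (L + C + G)/365. The extremes are 1 − 98/365 = 73% and 1 − 280/365 = 23%.

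Day only missing, by direct count over the same grid: after chemotherapy start in 51%, 5% and 0% for L = 14, 28 and 56; after chemotherapy end in 0%.

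After avelumab start: 0% in every setting.

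**Where the date is used**

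OS, PFS, PFS2 and DOT start at first avelumab, OS 2 at first chemotherapy, and DOR at first response (SAP 8.2.1–8.2.2). The measures for subsequent treatment start at that treatment. No subgroup in SAP 5.3 and no characteristic listed in SAP 2.2 or protocol section 8 is derived from the diagnosis date.

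**The case against.** The strongest reply is that nothing named in the plan depends on this date. The listed characteristics include the chemotherapy-to-avelumab interval but no interval from diagnosis. One may appear in the table shells, which are in a separate file. This stands, and it keeps the point minor. It does not defend the rules: four rules written for one date imply an intention to use it, most naturally in the baseline description of SAP 8.2.4.

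Protocol 9.6 also plans coherence tests and queries, and section 9.9.2 has missing items pursued with the site. These act on recorded data and do not constrain a date imputed later.

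Several stronger readings are tempting, and the documents do not support them.

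- A reader might infer that survival results are shifted. They are not, since no time origin uses diagnosis.
- A reader might infer that every affected interval becomes zero or negative. Time since diagnosis is never negative at avelumab start, and a diagnosis in a year well before chemotherapy, as with older localized disease, keeps a positive interval shortened by less than a year.
- A reader might infer that retrospective patients are hit harder. Diagnosis precedes inclusion for everyone, and protocol 9.4 takes the data from medical records for all. No frequency of partial dates is given for either group.
- A reader might infer a minimum size for the same-year error from a typical 4–6 cycle course. SAP 5.3 also allows fewer than 4 cycles and delays under 4 weeks. With an assumed 3-week cycle, 3 × 3 + 3 = 12 weeks is possible, so no such floor exists.

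**Conclusion.** The rules are wrong as written for a maintenance cohort. The same-year rule always contradicts the eligibility sequence. The 31 December and month-end rules do so under the conditions above. The bias is one-directional: diagnosis is never placed too early.

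The consequence is small. It is limited to any descriptive time since diagnosis, or diagnosis-to-chemotherapy interval, that may be tabulated. The 84–96% and 46–79% figures describe year-only advanced-disease records under the assumed lags, not the share of the cohort, which cannot be worked out from the documents. The conclusion rests on reading treatment start as avelumab start, which SAP 8.2.1 and 8.2.2.1 support but 11.1.2 does not state.

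**What to change.** Amend the diagnosis block of SAP 11.1.2 as follows.

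1. Define treatment start, and say whether the rules cover the localized diagnosis, the advanced or metastatic diagnosis, or both.
2. Require that an imputed advanced-disease diagnosis be no later than the first dose of first-line chemotherapy. For a localized diagnosis, require that it be no later than the first localized treatment or the advanced-disease diagnosis, whichever is earlier.
3. Subject to that cap, use a midpoint: the 15th when the day is missing, 1 July when month and day are missing. SAP 11.1.2 already uses the 15th for partial last-dose dates and 1 July for birth dates, and weighs other known dates for the former.
4. Query any recorded diagnosis month or year later than that of chemotherapy start, instead of imputing it.
5. Report the number of imputed dates and how often the cap applied.

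By construction, the cap removes every imputed diagnosis after chemotherapy start. In the worked sequences, the first error falls from 164 to 26 days (capped at 10 February 2021), the second from 235 to 28 (capped at 7 June 2021), and the fourth from 21 to 5 (15 May 2021). The third goes the other way: 1 July 2020 is 142 days early instead of 41 late. The cap is therefore the essential part, and the midpoint is a convention that stops all errors sharing one sign.

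The cost is SAP wording, a short derivation with two caps, and one added query check. The dates needed are already collected. The downside is that diagnosis-to-chemotherapy time is set to zero whenever the cap binds, which is the reason for step 5.
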